Study treatment discontinuation	When the subject permanently stops taking study treatment prior to the defined study treatment completion date
Subject	A trial participant (can be a healthy volunteer or a patient)
Subject number	A unique number assigned to each subject upon signing the informed consent. This number is the definitive, unique identifier for the subject and should be used to identify the subject throughout the study for all data collected, sample labels, etc.
Treatment number	A unique identifier assigned in non-randomized studies to each dosed subject, corresponding to a specific treatment arm
Variable	A measured value or assessed response that is determined in specific assessments and used in data analysis to evaluate the drug being tested in the study
Withdrawal of consent (WoC)	Withdrawal of consent from the study occurs only when a subject does not want to participate in the study any longer and does not allow any further collection of personal data

Commercially Confidential Information

Commercially Confidential Information

Commercially Confidential Information

Commercially Confidential Information

Commercially Confidential Information

Protocol Synopsis

Protocol number	CLIK066X2204
Full Title	A 12-week randomized, patient and investigator blinded, placebo-controlled, parallel group study to investigate the efficacy of LIK066 in obese patients with non-alcoholic steatohepatitis (NASH)
Brief title	Study to assess efficacy of LIK066 in obese patients with non-alcoholic steatohepatitis (NASH)
Sponsor and Clinical Trial Phase	Novartis Phase II
Intervention type	Drug
Study type	Interventional
Purpose and rationale	The purpose of this study is to assess the effects of LIK066 on liver function tests (LFT) and a variety of metabolic and inflammation biomarkers in patients with phenotypic non-alcoholic steatohepatitis (NASH) after 12 weeks of treatment. Data from this study will be used to support further development of LIK066 in the treatment of patients with NASH.
Primary Objective(s)	
 To determine the effect of LIK066 on Liver Function test (circulating ALT) after 12 weeks of treatment

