6.6 Permitted dose adjustments and interruptions of study treatment

Investigational treatment dose adjustments and/or interruptions are not permitted.

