7.2 Discontinuation of study treatment

Discontinuation of study treatment for a patient occurs when study treatment is stopped earlier than the protocol planned duration. Discontinuation of study treatment can be decided by either the subject or the investigator.

Study treatment must be discontinued under the following circumstances:

- Patient decision - patients may choose to discontinue study treatment for any reason at any time.
- The investigator believes that continuation would negatively impact the safety of the patient or the risk/benefit ratio of trial participation.
- Any protocol deviation that results in a significant risk to the patient's safety
- Pregnancy (see [Section 8.6](#) (Safety) and [Section 9.6](#) (Pregnancy reporting))
- Discontinuation may be considered when patients have to be treated by prohibited medications on a case by case basis.

- Use of prohibited treatment as per recommendations in [Table 5-1](#)
- Hypersensitivity (CTCAE grade 2 or higher) reaction to LIK066 requiring intervention.
- Clinically significant diarrhea, suspected to be related to the study drug and not responsive to recommended management per SOM that may put the patient at risk (identified by investigator after consultation with the sponsor)
- Symptomatic orthostasis confirmed by repeated orthostatic blood pressure changes (more than a 20 mmHg drop in systolic or 10 mmHg drop in diastolic blood pressure and increase in heart rate >20 bpm (compared to sitting results) when blood pressure and pulse are taken after at least 3 minutes (standing)
- Clinically significant urinary tract or genitourinary infections, at the discretion of the investigator and consultation with the sponsor
- Clinically symptomatic hypoglycemia confirmed by repeated blood glucose levels (<56 mg/dL)
- Ketoacidosis (symptoms of ketoacidosis include nausea, vomiting, abdominal pain, unusual tiredness and trouble breathing) confirmed by blood pH and ketones.
- For ALT, AST, total bilirubin and/or alkaline phosphatase elevations mandating study treatment discontinuations, please refer to [Section 9.3](#) and [Table 9-1](#) and [Table 9-2](#) for further instructions and monitoring. Of note, ALT and AST are abnormal at baseline in this study. Thus only elevation to >2X of the baseline value will trigger events listed in [Section 9.3](#).
- Adverse events, abnormal laboratory values or abnormal test result that indicate a safety risk to the patient, in the opinion of the investigator

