9.8.3 Orthostatic hypotension

Because orthostatic hypotension is a potential risk of LIK066 treatment, orthostatic blood pressure readings will be recorded throughout the study as shown in the [Assessment schedule](#).

Any patient with clinically significant symptomatic orthostasis (more than 20 mmHg drop in systolic or 10 mmHg drop in diastolic blood pressure and increase in heart rate >20 bpm) will have the study treatment placed on hold. In addition, individuals with orthostasis will be treated with volume replacement according to standard of care (refer to [Section 7.2](#) (Discontinuation of study treatment)).

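### Section 6.6 of the protocol bans every treatment interruption, while 8.6.7, 9.4 and 9.8.3 each require a temporary hold for safety

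*Protocol*

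**What the plan says.** Protocol 6.6 is a single visible sentence: "Investigational treatment dose adjustments and/or interruptions are not permitted". It carries no exception and no redaction mark.

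Protocol 9.8.3 gives this trigger for orthostasis that is symptomatic and clinically significant: "more than 20 mmHg drop in systolic or 10 mmHg drop in diastolic blood pressure and increase in heart rate >20 bpm". The action it sets is that such a patient "will have the study treatment placed on hold". It then refers the reader to 7.2.

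Protocol 7.2 opens its mandatory list with "Study treatment must be discontinued under the following circumstances". One entry is "Symptomatic orthostasis confirmed by repeated orthostatic blood pressure changes", with the same thresholds ("10 mmHg drop in diastolic blood pressure and increase in heart rate >20 bpm (compared to sitting results") and a standing time of at least 3 minutes. The glossary defines discontinuation of study treatment as permanent: "When the subject permanently stops taking study treatment prior to the defined study treatment completion date".

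Other sections also provide for a temporary stop:
- 8.6.7 requires one after a positive urine pregnancy test, until the serum test is negative.
- Table 9-4 in 9.4 requires one when a creatinine rise above 50% cannot be confirmed within 24-48 hours.
- 9.3 and Table 9-4 ask the investigator to consider one for certain liver and renal findings.
- 9.1 includes interruption and dose increase or reduction among the actions that may be taken for an adverse event.

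**The concern.** A mandatory safety rule should be one that a site can obey without breaking another rule. Here a site that holds drug under 8.6.7, 9.4 or 9.8.3 departs from 6.6, and a site that obeys 6.6 departs from the safety section.

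Read literally, 6.6 leaves two options when one of these signals appears: carry on dosing or stop for good. Neither is what the safety sections ask for. Carrying on means continued exposure while a possible pregnancy, a possible renal injury or symptomatic orthostasis is being checked. Stopping for good means losing treatment over a signal that the repeat test may not bear out.

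The signals are not remote from this drug. Protocol 3.6 names postural hypotension from volume depletion and renal toxicity among the possible risks, and it warns of unknown risk to a fetus.

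**Working it through.** The plan gives no figure to reproduce, and no sample size or error rate is involved. The check sets the sections side by side.

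**Step 1. Instructions to stop temporarily that are mandatory.**
1. 8.6.7: positive urine pregnancy test. The stop ends with a negative serum result, so it is temporary by its own terms.
2. 9.4, Table 9-4: creatinine rise above 50% that cannot be confirmed in 24-48 hours. The stop lasts until the patient can be evaluated further, so it too is temporary.
3. 9.8.3: clinically significant symptomatic orthostasis. The action is a hold.

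**Step 2. Instructions to consider a temporary stop.**
1. 9.3, follow-up of liver laboratory triggers: a confirmed elevation.
2. 9.3, Table 9-2: any adverse event that may indicate liver toxicity.
3. 9.4, Table 9-4: creatinine rise above 50%.
4. 9.4, Table 9-4: rise in the albumin- or protein-creatinine ratio, or proteinuria.

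**Step 3. Count.** 3 mandatory + 4 to consider = 7 instructions, in four sections (8.6.7, 9.3, 9.4, 9.8.3). Exceptions stated in 6.6: 0. The action list in 9.1 is separate from this count. It provides for interruption and dose change in general terms, and 6.6 excludes both.

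**Step 4. Can the mandatory holds be read as discontinuation, which 6.6 does not forbid?** No. The glossary makes discontinuation permanent. The holds in 8.6.7 and 9.4 have an end point written into them, and 9.8.3 speaks of a hold. The conflict with 6.6 is therefore direct for all three. For the four instructions to consider, it arises only if the investigator chooses to interrupt.

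**Step 5. Do 7.2 and 9.8.3 conflict with each other on orthostasis?** Not necessarily. 7.2 asks for confirmation by repeated readings and 9.8.3 does not, and 9.8.3 points to 7.2. Holding first and discontinuing if repeat readings confirm satisfies both. The difficulty is that 6.6 forbids the hold on which this sequence depends.

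**Step 6. The trigger.** Both sections join a systolic limb, a diastolic limb and a heart-rate limb by *or* and then *and*, without showing the grouping. The more natural reading is (systolic or diastolic) and heart rate. The alternative, systolic or (diastolic and heart rate), gives a different answer only when systolic pressure falls by more than 20 mmHg without a heart-rate rise above 20 bpm. It is also unclear whether *more than* carries over to the diastolic 10 mmHg. Both ambiguities are shared by the two sections.

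**The case against.** The strongest reply is that no patient is left unprotected. Protocol 13.1 expects the investigator to take any immediate action a subject's safety requires, including one that deviates from the protocol, and that covers a hold. Protocol 7.2 requires discontinuation whenever "The investigator believes that continuation would negatively impact the safety of the patient". This stands as mitigation. It does not remove the conflict: under 13.1 a hold that the protocol itself orders would still be a deviation, and the judgment entries in 7.2 lead to discontinuation, not to a pause.

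A second reply is that a specific safety rule overrides a general one. That is how most sites would probably act, but the visible text states no such precedence.

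Some stronger readings are tempting and are not supported:
- A reader might infer that 6.6, 7.2 and 9.8.3 give three rival instructions for one orthostasis trigger. They do not. 6.6 is a general rule with no orthostasis trigger, and 7.2 and 9.8.3 fit together as hold, then discontinue if confirmed.
- A reader might infer that the trigger is inconsistent between sections. The limbs are joined in the same way in both, and there is a natural reading. How often the alternative reading would matter cannot be derived, since the documents give no event rates.
- A reader might infer that no restart rule exists. Text after the list in 7.2 is redacted, and detailed instructions for taking study drug sit in the Site Operations Manual, so this cannot be shown.
- A reader might infer that holds would drop patients from the PD analysis set, which 11.1 limits to patients without deviations of relevant impact. The documents do not say how a safety hold would be classified, and the SAP section on analysis sets is redacted.

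**Conclusion.** Protocol 6.6 is wrong as written. It bars all interruptions, while three mandatory holds (8.6.7, 9.4, 9.8.3) and four optional ones (9.3, 9.4) depend on interruption being allowed, and 9.1 lists interruption and dose change as ordinary actions. The contradiction is visible in unredacted text and rests on one assumption only: that nothing outside the documents, such as the Site Operations Manual, qualifies 6.6. Even if something did, the protocol sentence itself would still need correcting.

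The consequence is for conduct and safety instructions. No bias between arms, change in adverse event counts, or effect on power or error rate is claimed, and 13.1 and 7.2 limit the risk to patients. The unstated sequence in 9.8.3 and the ungrouped trigger are minor points of clarity.

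**What to change.** 1. Amend 6.6 to read, in substance: *not permitted except for safety holds required or allowed in Sections 8.6.7, 9.3, 9.4 and 9.8.3*.
2. Align the adverse event action list in 9.1 with the amended 6.6, so that interruption refers to those holds and dose increase or reduction is not offered as an option if it remains barred.
3. As a minor clarification, state in 9.8.3 that treatment is held at the first qualifying reading and discontinued under 7.2 if repeat readings confirm. Keep the qualifier that the orthostasis be clinically significant, so that the set of patients to be held does not change.
4. Have the sponsor confirm the grouping of the trigger, and whether the diastolic limb is >10 or >=10 mmHg. Then use one bracketed wording in 7.2 and 9.8.3. The sponsor should settle the diastolic limit explicitly, because either choice could move the threshold.

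The cost is a few wording edits in an amendment, with no new data, visits or analyses. The downside is possibly a few more temporary holds.

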9.8.4 Fournier's gangrene

FDA recently issued a safety warning about reported occurrences of a rare but serious and life-threatening infection of the genitals and area around the genitals, necrotizing fasciitis of the genitalia and perineum, commonly referred to as Fournier's gangrene (FG), associated with the SGLT2 inhibitor class of drugs for the treatment of type 2 diabetes. Outcomes have included hospitalizations, multiple surgeries, and death. This serious medical condition requires urgent antibiotics and surgical intervention. While no such cases have been reported with clinical trials of LIK066, patients who present with pain, tenderness, erythema or swelling of the genitals and the perineum along with fever or malaise, should be evaluated for necrotizing fasciitis of the genitals and perineum. If FG is suspected, LIK066 treatment should be discontinued and appropriate medical (including broad-spectrum antibiotics) and surgical treatment initiated as appropriate.

In general, subjects receiving LIK066 should be instructed to pay attention to genital hygiene and have appropriate hydration to reduce the risk of development of genitourinary infections including Fournier's gangrene.

10 Data review and database management

10.1 Site monitoring

Before study initiation, at a site initiation visit or at an investigator's meeting, a Novartis representative will review the protocol and data capture requirements (i.e. eSource or eCRFs) with the investigators and their staff. During the study Novartis employs several methods of ensuring protocol and GCP compliance and the quality/integrity of the sites' data. The monitor will visit the site to check the completeness of subject records, the accuracy of data capture / data entry, the adherence to the protocol and to Good Clinical Practice, the progress of enrollment, and ensure that study drug is being stored, dispensed, and accounted for according to specifications. Key study personnel must be available to assist the monitor during these visits.

The investigator must maintain source documents for each subject in the study, consisting of case and visit notes (hospital or clinic medical records) containing demographic and medical information, laboratory data, electrocardiograms, and the results of any other tests or assessments. All information on CRFs must be traceable to these source documents in the subject's file. The investigator must also keep the original informed consent form signed by the subject (a signed copy is given to the subject).

The investigator must give the monitor access to all relevant source documents to confirm their consistency with the data capture and/or data entry. Novartis monitoring standards require full verification for the presence of informed consent, adherence to the inclusion/exclusion criteria, documentation of SAEs, and the recording of data that will be used for all primary and safety variables. Additional checks of the consistency of the source data with the CRFs are performed according to the study-specific monitoring plan. No information in source documents about the identity of the subjects will be disclosed.

10.2 Data collection

Designated investigator staff will enter the data required by the protocol into the Electronic Case Report Forms using fully validated software that conforms to 21 CFR Part 11 requirements. Designated investigator site staff will not be given access to the EDC system until they have been trained. Automatic validation programs check for data discrepancies and, by generating appropriate error messages, allow the data to be confirmed or corrected before transfer of the data to the CRO working on behalf of Novartis. The Investigator must certify that the data entered into the Electronic Case Report Forms are complete and accurate. After database lock, the investigator will receive copies of the subject data for archiving at the investigational site.

Data not requiring a separate written record will be defined in the Site Operations Manual and [Assessment schedule \(Section 8.1\)](#) and can be recorded directly on the CRFs. All other data captured for this study will have an external originating source (either written or electronic) with the CRF not being considered as source.

All data should be recorded, handled and stored in a way that allows its accurate reporting, interpretation and verification.

10.3 Database management and quality control

Novartis (or a designated CRO) will review the data entered into the CRFs by investigational staff for completeness and accuracy and instruct the site personnel to make any required corrections or additions. Queries are sent to the investigational site using an electronic data query. Designated investigator site staff is required to respond to the query and confirm or correct the data. If the electronic query system is not used, a paper Data Query Form will be faxed to the site. Site personnel will complete and sign the faxed copy and fax it back to Novartis (or designated CRO) who will make the correction to the database. The signed copy of the Data Query Form is kept at the investigator site.

Concomitant medications entered into the database will be coded using the WHO Drug Reference List, which employs the Anatomical Therapeutic Chemical classification system. Medical history/current medical conditions and adverse events will be coded using the Medical dictionary for regulatory activities (MedDRA) terminology.

Laboratory samples will be processed centrally and the results will be sent electronically to Novartis (or a designated CRO).

ECG readings will be processed centrally and the results will be sent electronically to Novartis (or a designated CRO).

Randomization codes and data about all study drug(s) dispensed to the patient and all dosage changes will be tracked using an Interactive Response Technology (IRT). The system will be supplied by a vendor, who will also manage the database. The database will be sent electronically to Novartis (or a designated CRO).

MRI data will be collected by the sites and will be transferred to imaging CRO for analysis. The data will then be electronically sent to Novartis.

Each occurrence of a code break via IRT will be reported to the clinical team and monitor. The code break functionality will remain available until study shut down or upon request of Novartis.

The occurrence of relevant protocol deviations will be determined. After these actions have been completed and the database has been declared to be complete and accurate, it will be locked and the treatment codes will be unblinded and made available for data analysis. Any changes to the database after that time can only be made after written agreement by Novartis management.

10.4 Data Monitoring Committee

Not required.

10.5 Adjudication Committee

An Adjudication Committee will be established to assess suspected cases of ketoacidosis as described in the SOM.

11 Data analysis

The analysis will be conducted on all subject data at the time the trial ends. Any data analysis carried out independently by the investigator should be submitted to Novartis before publication or presentation.

11.1 Analysis sets

For all analysis sets, patients will be analyzed according to the study treatment received. The safety analysis set will include all patients who received any study drug.

The PK analysis set will include all patients with at least one available valid (i.e. not flagged for exclusion) PK concentration measurement, who received any study drug and with no protocol deviations that impact on PK data.

The PD analysis set will include all patients with available PD data and no protocol deviations with relevant impact on PD data.

11.2 Subject demographics and other baseline characteristics

All data for background and demographic variables will be listed by treatment group and subject. Summary statistics will be provided by treatment group.

Relevant medical history, current medical conditions, results of laboratory screens, drug tests and any other relevant information will be listed by treatment group and patient.

11.3 Treatments

Data for study drug administration and concomitant therapies will be listed by treatment group and patient.

11.4 Analysis of the primary variable(s)

The primary objective of this study is to assess the efficacy of LIK066 on ALT in NASH patients during 12 weeks of treatment.

11.4.1 Primary Variable(s)

Change from baseline to Week 12 in ALT is the primary efficacy variable. 'Baseline' is defined as the mean of ALT levels at baseline (V101) and pre-dose (V201) visits.

11.4.2 Statistical model, hypothesis, and method of analysis

Commercially Confidential Information

11.4.3 Handling of missing values/censoring/discontinuations

Commercially Confidential Information

11.4.4 Sensitivity analyses

Commercially Confidential Information

Commercially Confidential Information

11.5 Analysis of secondary variable(s)

11.5.1 Efficacy / Pharmacodynamics

The secondary PD variables of this study are:

- Intrahepatic lipid: Percent (%) Liver fat as measured by Magnetic Resonance Imaging (MRI).
- Anthropometric assessments: Weight, BMI, waist-to-hip (WTH) ratio
- AST: Change from baseline to week 12
- Non-invasive markers of liver fibrosis:
 - Enhanced liver fibrosis panel (ELF)

Baseline for all secondary parameters is defined as the last measurement prior to the first dose except for AST where baseline is the mean at baseline (V101) and pre-dose (V201) visits.

Commercially Confidential Information

11.5.2 Safety

Vital signs

All vital signs data will be listed by treatment group, patient, and visit/time and if ranges are available abnormalities (and relevant orthostatic changes) will be flagged. Summary statistics will be provided by treatment and visit/time.

ECG evaluations

All ECG data will be listed by treatment group, patient and visit/time, abnormalities will be flagged. Summary statistics will be provided by treatment and visit/time.

Clinical laboratory evaluations

All laboratory data will be listed by treatment group, patient, and visit/time and if normal ranges are available abnormalities will be flagged. Summary statistics will be provided by treatment and visit/time. Selected lab markers such as AST, bilirubin, ALP, GGT, creatinine and BUN will be analyzed using the repeated measures ANCOVA as described in [Section 11.4.2](#).

Adverse events

All information obtained on adverse events will be displayed by treatment group and patient.

The number and percentage of patients with adverse events will be tabulated by body system and preferred term with a breakdown by treatment. A patient with multiple adverse events within a body system is only counted once towards the total of this body system.

